5.7.2 Data Collection and Management

De-identified data will be stored in a clinical trial management system. Data and statistical management will be contracted to an organization with experience managing academic clinical translational trials.

5.7.3 Data and Safety Monitoring

We will engage in proactive site monitoring through the Office of Clinical Research (OCR) through the National Institutes of Mental Health (NIMH). This service will be provided prior, during and after the study to ensure that Good Clinical Practice is maintained. Representatives from the office will arrange site visits with our team.

The OCR will oversee the creation and maintenance of a data safety monitoring board (DSMB). The DSMB will be comprised of an independent group of researchers and experts based out of the NIMH. Its role will be to monitor patient safety and treatment efficacy data during the conduct of this trial. Members of the group will meet regularly, approximately every six months in order to review safety, study conduct and progress.

The main responsibilities of the NIMH DSMB include, but are not limited to the following: review of protocols, consent procedures, consent forms, and safety plans prior to initiation of the study; monitoring of the progress of the study, including recruitment and retention of participants, adverse events, serious adverse events (SAEs), reasons for participant withdrawal, adherence to the timeline of the study, quality of data, and protocol violations; making directives about the continuation, modification, or termination of the study, based on the balance of adverse events and beneficial outcomes. Throughout the study, notification of any Serious Adverse Events (SAEs) as well as any proposed investigator-initiated changes in the protocol will be submitted to the NIMH DSMB. Based on its review of the protocol, the NIMH DSMB will identify the data parameters and format of the information to be regularly reported. The NIMH DSMB may at any time request additional information from the Principal Investigators.

All SAEs and adverse events (AEs will only be reported to the NIMH DSMB annually) will be tabulated and submitted to the central and local IRBs and NIMH DSMB in the triannual DSMB data reports or at the time of continuing review, IRB review of the study, although the NIMH DSMB can determine that more frequent meetings are indicated. Based on review of safety data, the NIMH DSMB will issue directives concerning the conduct of the study. Recommendation/directives made by the DSMB may include amending safety monitoring procedures, modifying the protocol or consent, terminating the study, or continuing the study as designed.

5.8 Outcome Analysis

5.8.1 Primary Outcome Analysis

Baseline variables will be summarized for each group by descriptive statistics. As per Senn et al. and Pocock et. al. [104, 105] significance tests between groups on baseline characteristics in a randomized trial are ill-advised and will not be done.

The primary efficacy analysis will be carried out in two stages. The first stage will test for non-inferiority of MST compared to ECT on remission. The second stage is a superiority comparison on cognitive function. If non-inferiority is established then, and only then, will the second stage analysis be carried out. This closed testing procedure ensures that the Type I error will not exceed the nominal alpha of 0.05.

Stage 1 Analysis

The hypothesis to be tested is $H_0: \pi_{ECT} - \pi_{MST} \geq 0.15$ versus $H_1: \pi_{ECT} - \pi_{MST} < 0.15$ where π_{ECT} and π_{MST} are the probabilities of remission in the ECT and MST groups respectively. The primary comparison will be a one-sided Z-test in difference of proportions, compared against the non-inferiority margin of 15%. The 15% non-inferiority margin was chosen as a remission rate of 35% remains clinically meaningful in this difficult to treat sample and still higher than more conventional, less invasive treatments for treatment resistant depression (e.g., rTMS at about 20 percent remission [106] and 14 percent with antidepressants [107]). The absolute risk difference (difference in proportions) will be calculated along with 90% and 95% confidence intervals, using standard normal approximations. Since intention to treat (ITT) analysis introduces a conservatism that is undesirable for non-inferiority trials both ITT (i.e. all randomized participants) and completer analyses (i.e. 8 treatments or met remission criteria) will be performed. The primary analysis for Stage 1 will be a completer analysis and a sensitivity analysis will be done secondarily. Inverse probability weighted methods will be employed in an attempt to attenuate the bias resulting from the improper sub-group that a PP results in. We plan to collect the primary outcome data from all patients regardless of treatment compliance to minimize missing data in the outcomes. If outcomes are missing in more than 5% of the patients in the ITT analysis, inverse probability weighting and multiple imputation approaches will be employed to assess and mitigate the effect of missing data. Multiple Imputation by Chained Equations (MICE) will be used to perform the imputations and the following variables will be used in the missing data model: number of failed antidepressant trials, duration of most recent depressive episode, number of major depressive episodes, benzodiazepine use, age, and presence of the other psychiatric comorbidities, e.g. anxiety, duration of illness, not taking psychiatric medication at baseline, treatment duration, and minority racial status. The number of replications for multiple imputations will be based on the proportion of data that is missing, e.g. 10% missing implies 10 replications. For the inverse probability weighting, weights will be estimated from a logistic regression model (with binary dependent variable: dropout vs not dropout) predicting probability of dropout. In order to have a correctly specified model, most of the baseline variables collected will be included (e.g. demographic and clinical characteristics, HRSD score, SSI score, CGI score, ATHF, BSI score, presence of medical and/or psychiatric comorbidities, etc.). It is only necessary for non-inferiority to be established in the unadjusted analysis described to proceed to the stage 2 analysis although additional secondary analyses of this outcome will be performed.

An adjusted analysis will be performed using generalized linear models for binary data. Study site will be included as well as clinical variables known to be associated with remission (see again Senn et al.[105] and Pocock et. al.[104]). The following variables will be included in the analysis, which have been shown to be related to response/remission in this population: number of failed antidepressant trials, duration of most recent depressive episode, number of major depressive episodes, and benzodiazepine use (in lorazepam equivalents). The purpose of the adjusted analysis is to ensure the non-inferiority finding is consistent between an unadjusted analysis and one in which predictors of outcome are controlled for. This consistency will be examined in two ways. First, the unadjusted odds ratio and 95% confidence interval will be compared with the adjusted for consistency. Second, the fitted logistic regression model will be used to estimate the probability of response for each subject. An adjusted difference in proportions will be estimated by averaging the predicted probabilities within group and taking the difference. A bootstrap will then be used to generate a distribution of this measurement from which the bias corrected percentiles can be obtained to compare with the 15% non-inferiority margin.

Stage 2 Analysis

In terms of cognitive superiority, we will use the autobiographical memory test (AMT). The binary outcome is defined as a worsening of $\geq 25\%$ on the AMT total score. The hypothesis to be tested is $H_0: \pi_{ECT} - \pi_{MST} = 0$ versus $H_1: \pi_{ECT} - \pi_{MST} \neq 0$ where π_{ECT} and π_{MST} are the probabilities of deterioration in the ECT and MST groups respectively. This primary analysis will be ITT. The hypothesis will be tested with a chi-square test. The absolute risk difference and 95% confidence interval will be computed using standard methods. Secondary analyses will follow a similar approach as in stage 1.

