5.0 APPROACH

5.1.1 Research Design and Methods

The trial will be registered in an international clinical trial registry (clinicaltrials.gov) and results will be reported in a manner consistent with the international CONSORT guidelines. The study will involve a randomized, double blind, parallel-group clinical trial with two treatment arms conducted at three leading academic institutions in North America: CAMH, University of Texas Southwestern in Dallas, and University of California, San Diego (UCSD). Based on our power analysis (Section 5.7.1), a total of 260 participants with depression will be randomized to receive MST or RUL-UB-ECT. We plan to enroll four to five participants per month across the three study sites over 54 months.

Treatment will be administered two to three days per week. Depression symptoms will be assessed with the 24-item Hamilton Depression Rating Scale (HRSD-24) [74] and suicidality will be assessed with the Scale for Suicidal Ideation (SSI) [69]. Remission will be defined as HRSD-24 ≤ 10 and a $> 60\%$ decrease in scores from baseline on two consecutive ratings. Once a participant reaches remission, a second rating to confirm remission will be conducted immediately before their next scheduled treatment. If remission is confirmed, they will then be considered a completer of the acute treatment course. Remission of suicidal ideation is defined as a score of 0 on the SSI. Therefore, there will be no specific minimum number of treatments that patients must receive to be classified as remitters. However, patients who do not meet remission criteria after 21 treatment sessions will be considered non-remitters and will cease treatment sessions. This maximum treatment number was chosen allowing for the possibility that MST may require more treatment sessions to achieve remission, similar to RUL-UB ECT [29-31]. The blind will not be broken to participants until the completion of the entire study. Following completion of the acute treatment course, participants who achieve response (defined as a 50% reduction in symptoms on the HRSD-24 from baseline) or remission will be referred to a maintenance treatment trial.

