5.7 Data Collection and Statistical Considerations

5.7.1 Power Calculations for primary hypotheses

The primary objective of this trial is to assess the efficacy and cognitive adverse effects of RUL-UB ECT and MST in patients with severe depression in a randomized, multi-centre, non-inferiority clinical trial. We will use a combined primary effectiveness endpoint: (1) MST will result in remission rates on the 24-item Hamilton Rating Scale for Depression (HRSD-24) that is non-inferior to that of RUL-UB ECT; **AND** (2) MST will have a superior cognitive adverse effect and tolerability profile compared to RUL-UB ECT assessed with the AMT. However, our sample size calculation will be based on non-inferiority trial calculations that are sufficiently large enough to minimize Type II error[103] and are consistent with previous large, multi-centre ECT trials[9]. RUL-UB ECT can achieve remission in about 50% of patients with a treatment resistant form of depression[10]. Non-inferiority trials such as this proposed study specify a tolerance threshold, with a tolerance of 15% denoting equivalence between the two treatments when the effectiveness of MST can be concluded to be not less than 35%. The total sample size is derived as a function of tolerance and power with a significance level of 0.05. Using these methods, a total sample size of 260 participants (130 per group) will yield 80% power to confirm a non-inferior difference in HRSD-24 remission rates of 15% between the two study groups. This sample size would also provide >95% power to detect a minimally important difference $\geq 25\%$ (absolute risk difference) change on the AMT total score. The primary analysis will proceed once a minimum of 260 participants achieve a clinically determined adequate trial of treatment. We will define a completer as any participant who has received an adequate trial of RUL-UB-ECT or MST as per the definition used in the literature by Sackeim and colleagues [10] (i.e., 8 treatments or meet remission criteria). The overall rate of dropout in a similar past trial at CAMH was less than 3 percent in those receiving fewer than 8 treatments. As such, the sample size of 260 completers will be attainable. Testing of the cognitive outcome will only proceed if non-inferiority is established on remission. This closed testing procedure will ensure the Type I error probability for these two outcomes does not exceed 0.05.

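### The deciding Stage 1 test is valid but forgoes precision from baseline data already collected, and the planned adjusted risk difference equals the raw one

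*Combined protocol and SAP*

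**What the plan says.** Section 5.8.1 (Stage 1 Analysis) tests whether remission on ECT exceeds remission on MST by 0.15 or more: "The primary comparison will be a one-sided Z-test in difference of proportions, compared against the non-inferiority margin of 15" percentage points. It then fixes which result counts: "It is only necessary for non-inferiority to be established in the unadjusted analysis described to proceed to the stage 2 analysis".

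The same section plans a secondary adjusted analysis as a consistency check. It includes site and four clinical variables described as related to response or remission in this population: "number of failed antidepressant trials, duration of most recent depressive episode, number of major depressive episodes, and benzodiazepine use (in lorazepam equivalents"). Baseline HRSD-24 is not listed. The adjusted difference in proportions is formed by averaging the fitted logistic probabilities within each treatment group and subtracting, and a bootstrap interval is then compared with the 15% margin.

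Baseline HRSD-24 is available for everyone, because eligibility requires a score of at least 21 (Sections 5.1.2 and 5.1.5). It also enters the outcome (Section 5.1.1): "Remission will be defined as HRSD-24 ≤ 10 and a $> 60\%$ decrease in scores from baseline on two consecutive ratings". In the analysis plan an HRSD score appears only in the model for the dropout weights.

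For size, Section 5.7.1 gives "a total sample size of 260 participants (130 per group") and says that this "will yield 80% power to confirm a non-inferior difference in HRSD-24 remission rates of 15% between the two study groups".

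**The concern.** Stage 1 carries the whole combined primary endpoint: if it fails, the cognitive comparison is not tested. Adjusting for prespecified prognostic baseline variables targets the same risk difference and the same margin with a smaller standard error. The plan names such variables but keeps them out of the deciding test, and gives no reason.

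Baseline HRSD-24 is a natural candidate because it sets how far a participant must improve. The two parts of the remission rule cross at a baseline of 25 (40% of 25 is 10). Above that, the cut-off of 10 binds: a baseline of 26 needs a fall of 16/26 = 62%, and a baseline of 40 needs 30/40 = 75%. Section 5.1.4 describes permuted blocks and states no stratification by site or severity, so the design does not visibly balance these factors.

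The secondary analysis might be expected to make up for this. As written, it cannot do so on the risk-difference scale.

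**Working it through.** **Inputs.** ECT remission is 50% ("RUL-UB ECT can achieve remission in about 50% of patients with a treatment resistant form of depression", Section 5.7.1). There are 130 participants per arm and the margin is 0.15. The power section says "The total sample size is derived as a function of tolerance and power with a significance level of 0.05" without giving sidedness; Section 5.8.1 makes the test one-sided. Equal true remission in the MST arm is my assumption, because Section 5.7.1 states no expected MST rate.

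**1. The plan's own figure.** Power = Φ(0.15/SE − 1.645).

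- Variance at 50%/50%: SE = √(2 × 0.25/130) = 0.0620, and power = Φ(2.419 − 1.645) = 78.0%. A full 80% would need 276 in total.
- Variance at 50%/35%: SE = √((0.25 + 0.2275)/130) = 0.0606, and power = Φ(2.475 − 1.645) = 79.7%. A full 80% would need 264 in total.
- One-sided 0.025 with 50%/50%: power is 67.7%, which does not match the plan.

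The stated 80% is therefore reproduced to within rounding at one-sided 0.05.

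**2. What adjustment could add.** If the covariates together explain a share R² of the outcome variance, SE is multiplied by √(1 − R²). The documents give no R², so the range below is assumed (50%/50%, one-sided 0.05).

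| R² | Power with 260 | Total N for 80% |
|---|---|---|
| 0 | 78.0% | 276 |
| 0.05 | 79.9% | 262 |
| 0.10 | 81.7% | 248 |
| 0.20 | 85.5% | 220 |

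On the 50%/50% calculation, 260 participants reach exactly 80% at R² of about 0.054.

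**3. Baseline HRSD-24 alone.** Assume baseline means of 29 to 33 and percentage change independent of baseline; neither is in the documents. The correlation with remission that arises through the cut-off of 10 is then about −0.09 to −0.16, so R² is 0.008 to 0.026. Power becomes 78.3% to 79.0%, a gain of 0.3 to 0.9 points. Most of any benefit would have to come from the joint covariate set.

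**4. The planned adjusted difference.** A logistic model with an intercept and an arm term satisfies the likelihood equations Σ(yᵢ − p̂ᵢ) = 0 within each arm. The mean fitted probability in an arm therefore equals that arm's observed remission proportion, whatever other covariates are included. Averaging within group and subtracting returns the raw difference exactly. In simulation the largest gap was 2 × 10⁻¹⁶. The same holds in every bootstrap resample, so the interval gains no precision.

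**5. Standardising over everyone.** Predicting each participant under both arms and averaging over the full set does use the covariates. In 4,000 simulated trials per setting, with one covariate:

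| R² | Variance, adjusted/unadjusted | Power, unadjusted → adjusted |
|---|---|---|
| about 0 | 1.00 | 78.6% → 78.0% |
| 0.06 | 0.95 | 79.0% → 80.4% |
| 0.10 | 0.90 | 79.0% → 82.1% |
| 0.17 | 0.85 | 80.0% → 85.2% |

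In a separate set of simulations with a true 15-point deficit, the adjusted method declared non-inferiority in 4.8% to 5.2% of trials, against a nominal 5%.

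**The case against.** A prespecified unadjusted difference in proportions is a legitimate primary analysis. It is unbiased under randomisation, its Type I error is correct, and its standard error already allows for chance imbalance. The plan also includes site in the secondary model, compares adjusted with unadjusted odds ratios (a real adjustment, though not on the scale of the margin), and uses baseline severity in its dropout weights. All of this stands. The loss is one of efficiency only.

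Three stronger readings are tempting, and the documents support none of them.

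- A reader might infer from 78.0% that the stated 80% is wrong. Another standard variance choice gives 79.7%, and Section 5.7.1 treats 260 as a minimum number of completers.
- A reader might expect a large gain. A multiple correlation of 0.5 (R² of 0.25) would give 87.5%, but nothing in the documents supports that value. A gain of 5 points already needs a correlation of about 0.37.
- A reader might think that chance imbalance is worse because treatment is known. Only the treating team is unblinded; participants and outcome raters are blinded (Section 5.1.4).

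It is also fair to say that changing the deciding analysis late in a trial whose enrolment was planned from March 2018 (Section 7.1.2) takes more care than editing a sentence. That bears on how the change is documented, not on whether it is sound.

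**Conclusion.** The point holds as an avoidable loss of precision, together with a secondary risk-difference analysis that does not adjust. It is not a validity failure.

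The size cannot be fixed from the documents. It is nil if the covariates are not prognostic, about 2 points of power at R² of 0.05, nearly 4 at 0.10 and about 7.5 at 0.20. The plan's own statement that the four predictors relate to remission makes some gain plausible but does not quantify it. These figures rest on equal remission of 50%, 130 per arm and one-sided 0.05.

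The equality of the within-group average and the raw difference needs no assumption beyond a logistic model fitted by maximum likelihood with an intercept and an arm term.

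The Stage 1 deciding analysis is in completers, a set defined after randomisation. Baseline adjustment does not remove selection bias from that set.

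**What to change.** Amend Section 5.8.1 before unblinding:

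- Make the Stage 1 deciding estimate the covariate-adjusted risk difference (ECT minus MST). Use a logistic model with arm, baseline HRSD-24 as a continuous term, site and the four predictors already listed.
- Predict each analysed participant under both arms, average over the whole analysis set, and take the difference.
- Compare a matching robust or bootstrap one-sided 95% upper bound with 0.15.
- Keep the unadjusted Z-test as the supporting analysis, and change the sentence that lets the unadjusted result alone open Stage 2.
- Replace the within-group averaging in the adjusted analysis with the same standardisation. Adding baseline HRSD-24 to that model without this change would gain nothing on the risk-difference scale.
- State a simple rule for missing baseline covariates, since these would now affect the decision.

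The cost is a dated amendment and a short piece of code, with no new data, no new patients and the same margin. The downside is a model-assisted primary estimate that is slightly less simple to present. If the covariates turn out not to be prognostic, the simulated cost was about half a point of power (78.6% against 78.0%).

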2.0 RISK/BENEFIT ASSESSMENT

2.1.1 Known Potential Risks

Based on safety studies over the last decade the known risks of the magnetically-induced seizures of MST are not greater than the known risks of electrically-induced seizures in ECT [71] and these are summarized below. The most likely additional risk with MST would be the risk of a missed seizure. However, missed seizures have a very low rate of occurrence from our CAMH open-label trial (i.e., <1/100 treatments). If the patient has clinically significant suicidal ideation with imminent intent or attempted suicide and requires hospitalization then [name] at CAMH, [name] at UT Southwestern or [name] at UCSD will be notified and the patient will be seen and assessed to determine the most appropriate plan of care. Patients may experience side-effects after each MST treatment. This can be caused by the treatment itself, the anesthetic medication, or not having anything to eat or drink for a long period of time. The most common side-effects are headache, dizziness, nausea or vomiting, muscle aches and fatigue. Treatment is available and will be provided by medical staff in the event of study-related injury or adverse event.

Known Risks of Seizure Therapies (ECT/MST) include:

- 1) Risks of general anesthesia, which involves about 1/100,000 treatments risk of death.
- 2) Risks of non-terminating seizures in about 1/100. This is usually treated with a medication given to the patient by the doctor monitoring the anesthesia.
- 3) Risks of decreased heart rate in about 1/100. This usually resolves on its own, but is monitored.
- 4) Risks of high blood pressure in about 1/100. This usually resolves on its own but is monitored. The anesthetist may also administer a fast-acting medication to reverse severe high blood pressure.

- 5) Risks of increased brain pressure in about 1/100,000. This effect, again, is usually temporary, and patients with conditions that would increase this risk are identified during the initial ECT screening.
- 6) Risks of temporary decline in blood oxygen during the seizure. Again, this is usually temporary and is monitored throughout the duration of the seizure.
- 7) Risks associated with a confusional state, including agitation and risk of injury due to falls from the ECT bed following the seizure. This is minimized by close supervision. In rare cases, brief sedation is used to avoid fall/injury.

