5.5 Discontinuation of Treatment Criteria

Participants will be discontinued from the treatment if they cannot continue the study safely based on any of the following criteria:

- (1) experience worsening in depression, defined as an increase in HRSD-24 score from baseline of more than 30% on two consecutive assessments;
- (2) experience clinically significant increase in suicidal ideation with imminent intent (based on the SSI) or attempt suicide;
- (3) develop clinically significant hypomanic or manic symptoms
- (4) withdraw consent
- (5) missed seizures (i.e. no induced seizure) on 2 consecutive treatment sessions despite parameter and anaesthesia optimization
- (6) non-compliant with treatment schedule (i.e. miss more than two scheduled treatments)

Participants who are non-compliant with the treatment regimen or who experience two missed seizures on two consecutive occasions despite optimization of anesthesia and treatment parameters will not be discontinued from the trial, but will continue to be followed and will complete assessments to the extent possible contingent upon patient agreement consistent with an intention to treat approach.

Patients who are not able to complete the biomarker testing will be able to complete the clinical portion of the trial and will not be excluded.

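### The completer set that alone decides Stage 1 non-inferiority is defined partly by remission, so early non-remitters drop out of the test; the 5% error rate is not assured if MST loses more of them

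*Combined protocol and SAP*

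**What the plan says.** Section 5.8.1 (Stage 1) makes the completer set primary: "The primary analysis for Stage 1 will be a completer analysis and a sensitivity analysis will be done secondarily". Section 5.7.1 defines the set: "We will define a completer as any participant who has received an adequate trial of RUL-UB-ECT or MST", meaning 8 treatments or remission. Section 5.8.1 repeats the rule: "completer analyses (i.e. 8 treatments or met remission criteria) will be performed". Section 5.1.1 adds that "there will be no specific minimum number of treatments that patients must receive to be classified as remitters".

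Section 5.5 lists reasons for stopping treatment that can apply before session 8. Among them are "experience worsening in depression, defined as an increase in HRSD-24 score from baseline of more than 30% on two consecutive assessments" and "missed seizures (i.e. no induced seizure) on 2 consecutive treatment sessions despite parameter and anaesthesia optimization", together with suicidality, mania, withdrawal of consent and missed sessions.

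On the decision rule, Section 5.8.1 says: "It is only necessary for non-inferiority to be established in the unadjusted analysis described to proceed to the stage 2 analysis". An all-randomised analysis is planned but has no stated role in the decision. Section 5.8.1 also says that the two-stage procedure holds Type I error at 0.05. Stage 2 is analysed by intention to treat, so the combined claim joins two populations.

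**The concern.** Take two participants who both stop at session 6, one remitted and one not. The first is in the primary analysis and the second is not. That is selection on the endpoint itself, which goes further than selection on adherence. Removing non-remitters raises the observed remission rate in each arm, and raises it more in the arm that loses more of them. If that arm is MST, the observed deficit shrinks and the non-inferiority test becomes too easy to pass.

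Section 5.7.1 starts the analysis only when at least 260 participants have had an adequate trial, so excluded failures are in effect replaced by further recruits. At stake are the trial's main efficacy claim and entry to Stage 2.

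**Working it through.** **Inputs from the documents.** ECT remission 50%; margin 15 points, so MST at 35% on the boundary; 130 per arm; significance level 0.05 with a one-sided Z-test; stated power 80%; early dropout below 3% overall in a past trial (Sections 5.7.1 and 5.8.1).

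**Assumed.** The split of early loss by arm, and that every early exclusion is a non-remitter. The documents give neither.

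**The plan's own figure.** Power = Φ(0.15/SE − 1.645). With both rates at 50%, SE = √(2 × 0.25/130) = 0.0620, and power = Φ(0.774) = 78.0%. With the variance taken at 50% and 35%, SE = 0.0606 and power = 79.7%. Either is close to the stated 80%. A one-sided 0.025 test gives 67.7%, so the plan is working at one-sided 0.05.

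**Effect of selection.** Let dE and dM be the fractions of each arm excluded as early non-remitters. The completer rates become pE/(1 − dE) and pM/(1 − dM), on 130(1 − dE) and 130(1 − dM) participants. The probability of declaring non-inferiority is Φ((0.15 − D)/SE − 1.645), where D is the completer difference.

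Example with dE = 0, dM = 6%, which is 3% overall: the MST rate is 0.35/0.94 = 37.2%, D = 12.8 points and SE = √(0.25/130 + 0.3723 × 0.6277/122.2) = 0.0619. The result is Φ(0.360 − 1.645) = 9.9%.

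Simulated false non-inferiority with true rates of 50% and 35% (nominal 5%); the formula agrees to within about 0.2 points:

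| Early loss ECT / MST | Overall loss | False non-inferiority, completers |
|---|---|---|
| 0 / 0 | 0% | 5.0% |
| 3% / 3% | 3% | 4.2% |
| 2% / 4% | 3% | 5.7% |
| 1% / 5% | 3% | 7.5% |
| 0 / 6% | 3% | 9.9% |
| 5% / 1% | 3% | 2.2% |
| 3% / 10% | 6.5% (above the documented rate) | about 10% |

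The all-randomised test stays at 5.0% or just below in each pattern, and a rule requiring both sets cannot exceed it.

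**A single data set.** Suppose 8 of 268 participants (3.0%) are lost early, all non-remitters on MST.
- Completers: 65/130 against 59/130. The difference is 4.6 points and the upper one-sided 95% limit is 14.8 points (p = 0.047), so non-inferiority is declared.
- All randomised: 65/130 against 59/138. The difference is 7.2 points and the limit is 17.2 points (p = 0.10), so it is not shown.

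**The case against.** The plan does not hide the problem. Section 5.8.1 acknowledges that the completer subset is a biased comparison, plans inverse probability weighting to reduce the bias, runs the all-randomised analysis, and collects outcomes whatever the compliance. Section 5.5 keeps non-compliant and missed-seizure participants in follow-up. Its reason for preferring completers, that intention to treat may be unsuitable for non-inferiority, is a recognised worry. All of this stands. It supports looking at both sets; it does not support letting the selected set decide alone.

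On weighting, a reader might infer that it is useless. No weighted analysis was run, so that is not shown. What the text supports is narrower. The weights use baseline variables while exclusion follows from on-treatment failure, so correction can only be partial. The gate is also the unadjusted test, and the plan does not say whether weighting applies to it.

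A reader might also infer that missed seizures will drive uneven loss, since Section 2.1.1 says "The most likely additional risk with MST would be the risk of a missed seizure". The same section puts the rate below 1 in 100 treatments, and stopping needs misses at two consecutive sessions. At 1% per session and independence, the chance within seven sessions is about 6 × 0.01² = 0.06%. Even with complete clustering it cannot exceed 7 × 1%/2 = 3.5%. Missed seizures should not be presented as the main driver.

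The worsening rule is narrow as well. With ratings every three treatments, only the ratings after treatments 3 and 6 can trigger it before session 8. The other stopping reasons carry no arm-specific expectation. Since the background sections tie reluctance about ECT to its cognitive effects, heavier ECT loss is also arguable.

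Finally, a reader might take an error rate of 10% or more as the expected one. Within the documented dropout rate, about 10% is reached only if every loss falls in MST.

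**Conclusion.** The structural fault is in the text: inclusion in the decisive set depends on the primary outcome, and no other analysis can overrule it. The stated control of Type I error at 0.05 is therefore not assured. At about 3% overall early loss, the false non-inferiority rate lies between roughly 2% and 9.9% depending on the split. Equal loss or heavier ECT loss is conservative, and loss heavier in MST inflates the error.

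These figures rest on assumed splits, on early exclusions all being non-remitters, and on true rates at the margin. The dropout figure comes from one past trial and may not match stopping under Section 5.5. The documents do not show that loss will be uneven or that the bias will favour MST. They show only that the decision rule has no protection if it does.

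**What to change.** In Section 5.8.1, state that non-inferiority is claimed and Stage 2 opened only if the upper one-sided 95% limit for ECT minus MST is below 15 points in both the all-randomised set and the completer set. In the all-randomised set, use the outcomes collected regardless of compliance, with the plan's own missing-data methods where they are absent. Report stops before session 8 by arm and reason.

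This changes wording only. With equal true rates of 50% and 3% loss per arm, simulated power falls from 77.0% (completers alone) to 75.8% (both sets). If ECT loses more, the rule keeps the completer set's already low power and does not restore it: about 66% at 5%/1% loss and 53% at 10%/3%. If MST loses more, the only power given up is what the completer set gained through the exclusions.
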